10.1.4. Informed Consent

➤ *General practice*

As outlined in section 9, the PHNs as the participating site will enter into a Standard Clinical Trial Agreement facilitated by the University of Sydney. General Practices have existing agreements to work with and share data with PHNs. General Practices participating in the trial will be listed on the Standard Clinical Trial Agreement applicable to their corresponding PHN region. General Practices, via the CTC, will be provided with an Information Statement about the study (Appendix 2A) outlining their roles and responsibilities and The Daffodil Centre research team (including the CTCs)'s role. The CTC will set out the pilot trial timeline and expectations of participating practices.

If allocated to the intervention arm, the practice will nominate a "Practice Champion" who will maintain ongoing contact with the CTC. This will involve monthly meetings via phone or zoom of 30 minutes to monitor progress outlined in Appendix 2A. If deemed appropriate by the PHN and general practice, in addition to consent obtained via the Standard Clinical Trial Agreement, the participating general practice will be provided with a Consent Form by the CTC (Appendix 3A) via an online developed REDCap portal.

Once consent is obtained from a General Practice, the practice will be provided with a unique identification number generated by the REDCap platform. General Practices will be identifiable to the core research team using this unique identification number which will be stored and accessible only to the core research team.

➤ *Individual GP and practice staff consent*

At least two GPs (2 FTE) from each practice need to participate in the pilot trial to achieve statistical power of the primary outcomes. Practice nurses, practice managers and other practice staff (e.g., receptionists) may also participate but not all staff are required to be part of the trial. Participating GPs and practice staff will be required to sign a consent form (Appendix 3B) to participate in trial activities, including baseline and post-trial evaluation surveys. The CTC will facilitate consent upon receiving participation confirmation. The CTC will email the General Practice (Appendix 1B) to seek individual participation and provide a Participant Information Statement (Appendix 2B) and a link to an online RedCap portal where consent may be provided (Appendix 3B). The CTC will be trained in undertaking responsible research and how to facilitate informed consent.

➤ *Individual patient consent*

Individual patient consent will not be sought for participation in the trial as no identifying information about patients will be collected and aggregate de-identified data reports will be used.

➤ *Withdrawal and termination*

Participation is voluntary. General practices can withdraw at any time without providing a reason. Individual GPs or practice staff within a participating practice may also withdraw at any time without providing a reason. Participants will be provided with a withdrawal of consent form by the CTC and the information will be recorded in the CTC project log, with the reason if provided. If an individual GP withdraws from the study the CTC will work with the participating general practice to identify an alternative replacement. If this is not possible, the general practice will be withdrawn from the study.

[figure not shown]

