10.2. Trial design

Following recruitment and informed consent, baseline data audits and practice surveys will be undertaken. After baseline data collection, practices will be allocated to the intervention and control arms. After an initial 6 months of usual care in all sites, the intervention will be delivered, and a mid-trial implementation survey undertaken with the intervention sites. At 12 months, the post-trial audit will be undertaken and post-trial surveys to measure the implementation effectiveness and secondary outcomes.

The 6-month period between recruitment and intervention delivery is being used as a **wash out period**. At recruitment, all practices may be exposed or most susceptible to incidental messaging relating to the NBCSP. The wash out period will ensure that we are best able to study the effects of the intervention. During this 6-month period, we will provide briefing and support to the intervention practices via the CTCs.

The flowchart of study procedures is provided in Figure 1 with the trial timeline outlined in the schedule of events ([see 10.8](#)). The dates displayed in the Figure 1 timeline are indicative and dependent on HREC approval. No activities will commence without HREC approval.

Figure 1. Trial Flowchart

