Data collection is facilitated by established Data Sharing Agreements between the PHN and general practices within their regions. The Agreement permits the extraction, sharing and use of de-identified practice data to the PHN to support the provision of health services and to improve health policies. The de-identified data may be disclosed to third parties to develop health prevention strategies or support research. PHNs are governed by the PHNs Cooperative's National Data Governance Committee and the PHNs National Data Governance Framework (28). The PHN has ownership and legal accountability of the management and use of the extracted and shared de-identified data through legislative and policy obligations. The software providers are governed by an organisational Privacy Policy related to the collection and storage of de-identified health data (28–30). The software providers encrypt de-identified data for transmission over secure channels.

General practices are required to display privacy notices within the practice of which Health Analytics Software they are using with disclosure that the information is secure and cannot identify patients. Patients may request that the general practice not collect or share their data. It is the responsibility of the general practices to obtain and manage patients' consent for their de-identified data to be shared beyond the practice CIS.

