10.4. Statistical analysis and data analysis

Descriptive statistics will be used to summarise the general practice characteristics for each trial arm and the outcome results.

Intention-to-treat analysis will be used, where all general practices allocated to the trial group will be included and analysed in the group that they were assigned. Both the primary and secondary outcomes will be compared between the intervention and control groups using poisson or negative binomial regression and generalised linear modelling with an identity link function and binomial family to estimate the odds ratio and difference in proportions respectively. The regression models will use generalised estimating equations with robust standard errors to allow for clustering by general practice and will adjust for the randomisation stratification factors (e.g., practice size, state, rurality, socioeconomic indexes for areas (SEIFA) (34)). Both the relative and absolute measures of the estimated intervention effect will be reported with their respective 95% confidence intervals, and a p values calculated from the logistic regression.

The intra-practice correlation, which quantifies the proportion of the total variation in the outcome attributable to between-cluster variation in the outcome will also be estimated using mixed effects modelling and reported with 95% confidence intervals.

Results from the IPSBQ will be analysed using descriptive statistics and multivariate analysis of variance (MANOVA) to assess difference in perceived barriers pre- and post-intervention implementation. Mediation analysis will be performed to assess the degree to which changes in specific barriers influence changes in behaviour (i.e. mechanisms of action).

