10.5. Allocation and blinding process

Randomisation for this study will be carried out at the level of general practice. Each practice will be allocated to the intervention or usual care arm using a random computer-generated sequence by the Daffodil Centre research team. To account for differences in region-specific NBCSP screening rates, the randomisation will be stratified by participating states (NSW and WA). In each state, the same number of practices will be allocated to the intervention and usual care arms. Accordingly, GPs, general practice staff and their patients will be assigned to the intervention or usual care arm based on the assignment of their general practice.

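### The rule that withdraws a whole practice when one GP leaves unreplaced is not reconciled with the intention-to-treat commitment and can cost randomised clusters

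*Protocol*

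**What the plan says.** The withdrawal paragraph of Protocol section 10.1.4 lets practices and individual staff leave at any time, and then covers the departure of one GP: "If an individual GP withdraws from the study the CTC will work with the participating general practice to identify an alternative replacement". The next sentence is: "If this is not possible, the general practice will be withdrawn from the study". The rule is the same in both arms. It is not limited to practices that fall below two GPs, and it does not say what happens to outcome data from a practice withdrawn in this way.

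The same section gives the reason for the two-GP minimum: "At least two GPs (2 FTE) from each practice need to participate in the pilot trial to achieve statistical power of the primary outcomes".

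On the analysis, section 10.4 specifies intention to treat, under which "all general practices allocated to the trial group will be included and analysed in the group that they were assigned". Section 10.5 fixes the unit: "Randomisation for this study will be carried out at the level of general practice". Section 10.2 fixes the order: "After baseline data collection, practices will be allocated to the intervention and control arms". Table 5 puts allocation in November 2023 and close-out in October 2024.

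Section 10.3.1 describes the data routes. Tests completed come from aggregate extracts held by the Primary Health Network (PHN): "Data collection is facilitated by established Data Sharing Agreements between the PHN and general practices within their regions". Recommendations come from a study tool built into Medical Director. Neither route is described as depending on one GP staying in the trial.

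**The concern.** The rule lets the trial team remove a randomised cluster after allocation for a reason that is not the practice's own decision. If the removed practice's data are then not extracted or not analysed, the analysis set is no longer the randomised set, and the commitment in section 10.4 cannot be met.

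Three things make this more than a matter of wording.

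- **The rule does not serve its stated reason.** Two GPs are required for power, but removing the practice turns the loss of one GP into the loss of a cluster. Read literally, a practice with four participating GPs also goes when one leaves.
- **The loss looks avoidable.** Both co-primary outcomes come through practice-level data systems, and section 10.1.3 excludes practices that do not share data with their PHN.
- **Retention depends partly on unblinded effort.** The coordinator helps to find the replacement and, under section 10.6, also holds the allocation codes.

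At stake are precision and, if losses are related to engagement and differ between arms, the comparability that randomisation provides.

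**Working it through.** **Reading the sections together.** Allocation in November 2023 and close-out in October 2024 leave about 11 months in which the rule can act on a randomised practice. Sections 10.1.4 and 10.4 agree only if withdrawal means the end of trial activities while extraction and analysis continue. The protocol does not say this.

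**Size of the trial.** The Synopsis gives 2 states x (25 + 25) = 100 practices, and section 10.1.2 gives up to 50 per arm. (Section 7 can be read as 50 per arm in each state; I use 50 per arm in total.) The protocol states no dropout rate, so there is no figure of its own to reproduce. All rates below are assumptions.

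**Step 1: clusters lost.** Let q be the chance that a GP withdraws and is not replaced, independently between GPs, and g the number of participating GPs. The chance that a practice is removed is 1 - (1 - q)^g.

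| q | g | Practices lost | Of 50 per arm |
|---|---|---|---|
| 2% | 2 | 4.0% | 2.0 |
| 5% | 2 | 9.75% | 4.9 |
| 10% | 2 | 19.0% | 9.5 |
| 5% | 3 | 14.3% | 7.1 |
| 5% | 4 | 18.6% | 9.3 |

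The more GPs a practice enrols, the more likely it is to be removed.

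**Step 2: power.** Using practice-level standardised effects and a two-sided 5% test, the effect detectable with 90% power at 50 v 50 is (1.960 + 1.282) x sqrt(1/50 + 1/50) = 0.648. At that effect, power is 0.87 with about 45 v 45 left (q = 5% in both arms, g = 2) and 0.83 with about 40.5 v 40.5 left (q = 10% in both arms). The cost in power is modest.

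**Step 3: bias under no effect.** Suppose fractions f1 (intervention) and f0 (control) are removed, and that removed practices lie D standard deviations below their arm's full mean. The retained mean in an arm rises by D x f/(1 - f), so

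bias = D x [f1/(1 - f1) - f0/(1 - f0)], and SE = sqrt(1/(50(1 - f1)) + 1/(50(1 - f0))).

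For 20% v 5% and D = 1: bias = 0.20/0.80 - 0.05/0.95 = 0.250 - 0.053 = 0.197; SE = sqrt(1/40 + 1/47.5) = 0.215; P(|Z + 0.197/0.215| > 1.96) = 0.151.

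For 10% v 5% and D = 0.5: bias = 0.5 x (0.111 - 0.053) = 0.029; SE = sqrt(1/45 + 1/47.5) = 0.208; rejection rate 5.2%.

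| Lost, intervention v control | D (SD) | Bias (SD) | Rejection rate, nominal 5% |
|---|---|---|---|
| Equal in both arms | same in both | 0 | 5% |
| 10% v 5% | 0.5 | 0.029 | 5.2% |
| 19% v 9.75% | 0.5 | 0.063 | 6.0% |
| 20% v 5% | 0.5 | 0.099 | 7.5% |
| 20% v 5% | 1 | 0.197 | 15.1% |

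Swapping the arms reverses the sign of the bias. The result therefore runs from nothing to material, depending on inputs that the protocol does not supply.

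**The case against.** The strongest reply is that withdrawal from the study is not the same as exclusion from the analysis. The sentence does not say that data are discarded or that extraction stops, and the handling of data from withdrawn clusters is often left to the statistical analysis plan. This stands in part. A reader might infer a flat contradiction, and the text does not prove one; it shows two statements left unreconciled. But the rule itself is in the protocol, and a site following it could stop extraction. An analysis plan could not recover data that were never extracted.

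A reader might also infer that the intervention arm will lose more practices, because it has monthly meetings and additional surveys. The documents do not support that. The rule is arm-neutral. The monthly meetings fall to the Practice Champion, not to the GP whose departure triggers the rule. Section 10.3.2 asks both arms for readiness questionnaires and invites clinicians in both to the awareness questionnaire, and section 10.10 sets one payment schedule. Coordinator support could equally improve retention among intervention practices. Some withdrawals may also come before allocation, where they do no harm to the randomised comparison.

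Finally, continued access to data is not automatic. Under sections 9 and 10.1.4, trial use of PHN data runs through a clinical trial agreement on which participating practices are listed. This objection stands, and the repair has to cover it.

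**Conclusion.** The point holds as an unreconciled conflict within the protocol: a rule imposed by the trial withdraws randomised practices, while the analysis section promises to keep them all. This does not depend on which arm loses more. The firm consequence is that each unreplaced GP can cost a cluster, about 10% of two-GP practices if 5% of GPs leave unreplaced. The loss of power is modest. Bias is possible but cannot be sized from the documents; across the unequal-loss cases shown it runs from about 0.03 to 0.20 SD, and it is zero if loss and deficit are the same in both arms. Those figures rest on assumed loss rates, an assumed deficit in the practices lost, and the reading that withdrawn practices drop out of the analysis. Replacement is attempted first and no withdrawal rate is known, so I rate this as something that should be fixed, not as a fatal flaw.

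**What to change.** Replace the final sentence of the withdrawal paragraph in section 10.1.4 with text to this effect: a GP's withdrawal ends that GP's participation only. If no replacement is found, the practice may stop trial activities but remains in its allocated arm. Extraction for both co-primary outcomes (PHN extracts for tests completed, the Medical Director tool for recommendations) continues to close-out unless the practice itself withdraws consent to data use. Practices lost are reported by arm with reasons.

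Naming both data routes matters: a sentence covering PHN data alone would leave the recommendation outcome unresolved. The clinical trial agreement that lists the practices, and the practice information statement, should be aligned so that a practice that stops activities is still covered for data extraction.

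The cost is one replaced sentence, matching lines in those two documents, and an ethics amendment. Both extractions are already planned, so no new data collection is needed.

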10.2. Trial design

Following recruitment and informed consent, baseline data audits and practice surveys will be undertaken. After baseline data collection, practices will be allocated to the intervention and control arms. After an initial 6 months of usual care in all sites, the intervention will be delivered, and a mid-trial implementation survey undertaken with the intervention sites. At 12 months, the post-trial audit will be undertaken and post-trial surveys to measure the implementation effectiveness and secondary outcomes.

The 6-month period between recruitment and intervention delivery is being used as a **wash out period**. At recruitment, all practices may be exposed or most susceptible to incidental messaging relating to the NBCSP. The wash out period will ensure that we are best able to study the effects of the intervention. During this 6-month period, we will provide briefing and support to the intervention practices via the CTCs.

The flowchart of study procedures is provided in Figure 1 with the trial timeline outlined in the schedule of events ([see 10.8](#)). The dates displayed in the Figure 1 timeline are indicative and dependent on HREC approval. No activities will commence without HREC approval.

Figure 1. Trial Flowchart

10.2.1. Intervention

The intervention is a multi-component, co-designed general practice-led intervention designed based on the evidence review and co-design process in the MAIL, GP & SCALE project.

A co-design process with GPs and practice staff (University of Sydney HREC 2022/755) assessed the intervention components to determine their practicability, acceptability, and perceived risk within general practice.

The intervention components are evidence-based and available from existing tools and systems. A brief outline of the intervention components is provided in Table 1 and further description in Appendix 6A. Where required, permission to use resources has been or will be sought, and the original sources will be appropriately acknowledged. Practices in both the intervention and control arms will have had some level of exposure to NBCSP related material prior to the intervention. Practices of the intervention arm will be actively supported and encourage to use materials and the evaluation will help determine whether it is the added support that improves the use of the available intervention components.

The intervention components will not change but the specific details may be refined over the trial. For example, GP education is a critical component of the intervention and existing educational webinars, resources and factsheets developed by Cancer Council Australia will be used (27). This component may be modified in future as information relating to the National Bowel Cancer Screening Program (NBCSP) are updated. The research team is aware that the NBCSP is currently undergoing review by the Department of Health and Aged Care that may impact the information provided to GPs and any education may require updating. The fundamental component will not change, and updates will be requested as future modifications for committee reviews.

Table 1 Intervention Components

Intervention component	Target	Description
Decision support tools	GPs and practice nurses	Decision-aids to support GPs/patients determine guideline-appropriate screening pathways.
Electronic point-of-care prompt	GPs	Electronic reminders integrated into CIS
Clinical system enhancement	Whole-of-practice	Use of cancer screening toolkit and clinical audits of patient data to identify under-screened patients and integrate practice CIS with the NCSR
Education	Whole-of-practice	Structured learning to educate on guideline-appropriate screening pathways and access to digital educational resources. This will include communication checklist to address screening barriers in non-participants.
CIS = Clinical Information System used by general practice to store and manage medical record data; GPs = general practitioners; NCSR = National Cancer Screening Registry		

